Study Protocol

Version 3

1 September 2018

Title:

A prospective double-blinded randomized controlled trial: assessment of immediate post-operative pain for FiLAV versus LIFT in the treatment of trans-sphincteric anal fistulas (LASERLIFT)

Design

A prospective, double-blinded, single credentialed colorectal surgeon, randomised controlled trial.

Settings

University Malaya Medical Centre, a tertiary teaching hospital.

Patients

Patients with high transsphincteric anal fistulas from January 2018 to December 2020

Intervention

Laser versus ligation of the fistula tract (LIFT) treatment

Primary Outcome Measure

Pain scores at rest and movement, at 6 and 24 hours post operatively will be measured using the visual analogue scale (VAS)

Secondary Outcome Measures

1. Operative time was measured in minutes at 0-, 3- and 6-months post-surgery
2. Continence assessed using Wexner at 0-, 3- and 6-months post-surgery
3. Quality of life assessed using SF-36 questionnaire at 0, 3 and 6 months post-surgery

Study Participants

Written informed consent was obtained from all patients all patients with high transphincteric anal fistulas were recruited into this trial.

Inclusion Criteria:

1. 18 – 75years
2. Able to give consent
3. Complex transphincteric fistulas; high transphincteric fistula, involving >30% of the external anal sphincter; Multiple fistulas; Anterior fistulas; Recurrent fistulas; Fistulas with seton

Exclusion Criteria:

1. Active perianal sepsis requiring drainage
2. Fistulas of non-cryptoglandular origin
3. - Crohn's, TB, malignancy
4. Expected lifespan <6 months
5. Pregnant women
6. Patient's with more than 1 definitive surgery done for the fistula before
7. Patient's with human immunodeficiency virus infection
8. Patient's with pre-existing chronic pain disorders
9. Patient's with Non-steroidal Anti-inflammatory Drug (NSAIDS) / Paracetamol allergies

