All patients' will be recruited from the surgical outpatient clinic at UMMC, where thorough history and clinical examination will be performed. Next patient will undergo an endo-anal ultrasound (EAUS - 2052 probe, GE healthcare BK Medical) by an experienced operator which then confirms the presence of a high transphincteric fistula and/or other branching tracts as per Park's fistula classification. An MRI would only performed if the EAUS was inconclusive. Baseline assessment of quality of life (QOL) using the SF36 questionnaire and continence using Wexner's scale will be done at the start upon recruitment. Patients will randomised into the laser or ligation arm using block randomisation via the Sealed Envelope program (<https://www.sealedenvelope.com>). Double blinding was achieved as patients and the data collector were blinded to the interventions.

Study Intervention And Post-Intervention Care

The laser procedure will be performed according to the technique described by Wilhelm et al. The internal and external opening will first be identified and the tract debrided. Upon activation a laser fibre (10Watt, 600nm, fibreglass length 1800nm, emitting a wavelength of 1470 nm, ENDOTEQ Medical Laser Germany GmbH) will release thermal energy of maximum 100 Joules homogeneously into the tract while being withdrawn at the speed of 1mm/s. The internal orifice was then closed with an interrupted absorbable stitch. For cases which required a core out, the external opening then left open to heal by secondary intention.

The LIFT procedure would be performed as first described by Rojanasakul et al 2007. The internal and external opening was first identified. A curvilinear incision made at the intersphincteric plane after identification of the internal and external opening. Dissection was then performed up until where the tract was encountered where it was then ligated as close as possible to the internal opening and a portion of the tract excised. The external opening was then curetted and tissue sent for histopathology studies. The skin then closed loosely with an interrupted absorbable suture.

Standardised analgesia (PO Celecoxib 40mg and PO Paracetamol 1g) will be served at exactly 6 hours post operatively. Pain scores was assessed by a blinded healthcare professional using the visual analogue scale (VAS) at 6 hours and 24 hours post operatively, at rest and on movement.

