Upon discharge, patients would be given oral antibiotics, PO celecoxib 40mg BD and PO paracetamol 1g QID for a week duration. All patients were reviewed at one week post-op for a wound assessment, and an official surgical consult at 1 month and 6 months post operatively.

Each surgical consult involved a history taking, clinical examination, QOL and continence assessment. Should there be any suspicion of a recurrence before 6 months they will be subjected to an EAUS. An MRI will be performed if the EAUS is inconclusive.

Study Definitions And Outcome Measures

Successful fistula healing is defined as complete wound healing and closure of all the external openings in combination with the cessation of outflow from the external openings at 6 months post operatively. Surgical failure was defined as failure of the fistula to close with persistence of discharge at 6 months post operatively. This encompassed the spectrum of wound infection, recurrence and technical failure.

Sample Size Justification

As there were no prior studies with the primary outcome on pain score prior to trial commencement, we proceeded to calculate the sample size based on the score obtained from a local audit. Then using the G-power software, to achieve an alpha error of 5%, confidence interval of 95%, power of 0.9 and a large effect size, 28 fistulas were required per arm.

Statistical Analysis

Analysis would be performed using SPSS Statistics for Mac (version 23 Inc., Chicago, IL, USA) with an intention-to-treat basis. Continuous variables will be presented as median and range or mean and standard deviation. Differences between groups can be compared using chi-square analysis or the Fisher exact test when data is categorical. While continuous variables can be compared using the student t-test or Mann-whitney based on normality of data distribution. We will consider data to be statistical significance if $p < 0.05$.

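### SF-36 and Wexner are scored at recruitment, but the analysis gives that score no role and does not say whether follow-up score or change is tested

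*Combined protocol and SAP*

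**What the plan says.** The Study Participants section provides for "Baseline assessment of quality of life (QOL) using the SF36 questionnaire and continence using" the Wexner scale at recruitment, described before the randomisation step. The Secondary Outcome Measures list has "Quality of life assessed using SF-36 questionnaire at 0, 3 and 6 months post-surgery" and "Continence assessed using Wexner at 0-, 3- and 6-months post-surgery". The Study Intervention And Post-Intervention Care section schedules "an official surgical consult at 1 month and 6 months post operatively" and adds: "Each surgical consult involved a history taking, clinical examination, QOL and continence assessment".

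For analysis, the Statistical Analysis section says that "Continuous variables will be presented as median and range or mean and standard deviation", and that "continuous variables can be compared using the student t-test or Mann-whitney based on normality of data distribution". It mentions no covariate, change score, repeated-measures model or main time point for these scores. The planned size is "28 fistulas were required per arm", derived for the pain score only.

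**The concern.** A score taken before treatment usually predicts the same score afterwards. A comparison that ignores it leaves explainable variation in the error term and gives no correction when the arms differ at recruitment by chance. With about 28 patients per arm, both matter more than they would in a large trial.

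The plan also leaves the tested quantity open. Follow-up score and change from recruitment both fit the wording, and their power differs widely with the correlation. An unstated choice can be made after the results are seen.

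At stake are the precision and pre-specification of the SF-36 and Wexner comparisons. The VAS pain analysis is not affected: the documents describe no pre-operative pain score to adjust for.

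**Working it through.** **The plan's own figure.** Taking a large effect to mean d = 0.8 (an assumption; no number is given), a one-sided 5% t-test with 90% power needs 28 per arm, which matches. A two-sided test would need 34. This concerns pain only; here 28 is used simply as the available number.

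**Inputs.** From the documents: n = 28 per arm, alpha 5%. Assumed: two-sided testing, one independent record per patient, equal SDs at recruitment and follow-up, no dropout, a true difference of 0.5 SD, and a baseline-to-follow-up correlation ρ from 0 to 0.7. The plan counts fistulas, so there may be fewer than 28 patients per arm; n = 20 is also shown.

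**Formulas.** Variance of the arm difference relative to the follow-up t-test:

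- change score: 2(1 − ρ)
- ANCOVA, including estimation of the slope: (1 − ρ²) × [1 + 1/(2n − 4)], with 2n − 3 degrees of freedom

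At n = 28 the bracket is 1 + 1/52 = 1.019. At ρ = 0.5 the ANCOVA factor is 0.75 × 1.019 = 0.764, a 24% cut in variance, equivalent to 28/0.764 = 36.6 per arm. The SE of the unadjusted difference is √(2/28) = 0.267 SD, so its 95% CI half-width is 2.005 × 0.267 = 0.536 SD. With ANCOVA at ρ = 0.5 it is 2.006 × 0.267 × √0.764 = 0.469 SD. Power is from the noncentral t distribution.

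| ρ | ANCOVA variance factor | ANCOVA CI half-width (SD) | Power: follow-up t-test | Power: change t-test | Power: ANCOVA |
|---|---|---|---|---|---|
| 0 | 1.019 | 0.54 | 45.1% | 25.5% | 44.4% |
| 0.2 | 0.978 | 0.53 | 45.1% | 30.6% | 45.9% |
| 0.3 | 0.927 | 0.52 | 45.1% | 34.2% | 47.9% |
| 0.5 | 0.764 | 0.47 | 45.1% | 45.1% | 55.6% |
| 0.6 | 0.652 | 0.43 | 45.1% | 53.8% | 62.3% |
| 0.7 | 0.520 | 0.39 | 45.1% | 66.0% | 72.2% |

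ANCOVA breaks even with the follow-up t-test where (1 − ρ²) × 1.019 = 1, at ρ about 0.14. The change score has the lower variance only where ρ > 2/1.019 − 1, about 0.96. With 20 per arm, power is 33.8% unadjusted against 34.1%, 35.7%, 41.9%, 47.6% and 56.6% for ANCOVA at ρ = 0.2, 0.3, 0.5, 0.6 and 0.7.

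**Non-normal scores.** The table does not apply to Mann-Whitney or to Wexner. Illustrative simulations at 28 per arm, with ρ and the 0.5 shift on the underlying normal scale, compare Mann-Whitney with Quade's rank-based ANCOVA. Wexner-like scores use an assumed 0 to 20 integer scale.

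| Scores | Mann-Whitney | Rank ANCOVA at ρ = 0.2, 0.3, 0.5, 0.6, 0.7 |
|---|---|---|
| Lognormal, log-SD 1 | 43 to 44% | 43.9, 45.9, 52.9, 58.5, 67.1% |
| Wexner-like, 50% zeros | 39 to 40% | 40.2, 41.1, 46.1, 50.3, 56.4% |
| Wexner-like, 80% zeros | 30% | 29.9, 30.5, 32.2, 34.2, 37.0% |

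On the lognormal scores linear ANCOVA reaches only 31%, 32%, 37%, 40% and 47%, below Mann-Whitney until ρ is about 0.7. Type I error of the rank method was 4.8% to 5.5%.

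**Chance imbalance (normal scores).** The baseline difference has SE 0.267 SD, so the probability that it exceeds 0.5 SD is 2Φ(−0.5/0.267) = 0.061. Given a 0.5 SD imbalance, as ρ goes from 0.2 to 0.7 the type I error runs from 5.9% to 17.7% for the follow-up t-test and from 15.6% to 9.1% for change; ANCOVA stays at 5%. Given 0.25 SD, all three are at about 5% or below.

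**The case against.** The strongest reply is that nothing here is invalid. The unadjusted test holds its error rate over all randomisations, the outcomes are secondary, and no power is promised for them. That stands, and it limits the weight of the point to efficiency and pre-specification.

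The benefit also rests on a correlation, SDs and an effect size that the documents do not give. True: at ρ = 0.5 the power gain is about 10 points for d = 0.5, 8 for d = 0.8 (84% to 92%) and under 5 for d = 0.3 (20% to 24%). The variance and CI figures do not depend on d and are the better summary. Even the adjusted comparison has only modest power at 0.5 SD.

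On wording, change is mentioned nowhere, so a comparison of scores at each time is the more natural reading. That is fair, but it is not stated.

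For skewed scores, the shortfall of linear ANCOVA comes from using means rather than ranks, not from adjusting: the unadjusted t-test on the same lognormal data has about 31% power. That is correct, and is why the rank version is the proper partner to Mann-Whitney.

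Finally, choosing the method by normality and testing several scores at several times raise issues of their own. Both are already in the plan and adjustment does not worsen them. Quade's method gives a test without an adjusted estimate or CI; that limitation remains for Wexner.

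**Conclusion.** The concern holds. The plan collects a baseline for both scales, gives it no role, and leaves open what is tested. Under normality with 28 patients per arm, adjustment costs at most 1.9% in variance (under one power point at d = 0.5), is negligible in effect near ρ = 0.2, and cuts variance by 24% at ρ = 0.5 and 48% at ρ = 0.7. For Wexner the gain depends on the share of zeros: at ρ = 0.5 it is about 6 to 7 power points with half zeros and about 2 with 80% zeros. The size of the gain in this trial is unknown because the correlation is unknown; the omission itself is plain from the text. This should be corrected, but it does not threaten the primary analysis.

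**What to change.** Add to the Statistical Analysis section:

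> Each SF-36 score will be compared between arms at each follow-up assessment by ANCOVA, with the follow-up score as outcome, arm and the patient's own recruitment score as covariates, and one record per patient. The adjusted difference and 95% CI will be reported. Where a score is judged non-normal on pooled data without arm labels, and for Wexner in all cases, a rank-based ANCOVA (Quade) on the recruitment score replaces Mann-Whitney, reported with medians and ranges by arm.

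Two clarifications are needed alongside it. If the month-0 score in the Secondary Outcome Measures is the recruitment score, say that it is the covariate and not a tested outcome. Reconcile the follow-up times, which are 3 and 6 months in that list but 1 and 6 months in the post-intervention care section, so that each follow-up assessment is defined. A line on how a missing recruitment score is handled would complete it.

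The cost is a few sentences. Both analyses run in SPSS version 23; the rank version needs only ranking, one regression and a comparison of residuals between arms. The 6-month comparison is scheduled in both places and needs no new data, visits or patients.
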